4.5.3 Primary Efficacy Endpoint Analysis Methods

The primary efficacy endpoint is ORR assessed by an IRC.

Patients will be analyzed according to their cohort/lymphoma subtype. For Cohort 3a patients who cross over from monotherapy to receive combination therapy, the CT/PET scan immediately preceding their first dose of combination therapy will be used for their baseline tumor assessment (and not the scan performed at the screening visit).

The number and percentage of patients with a CR or PR after initiation of treatment will be summarized by cohort. Ninety-five percent (95%) confidence intervals (CIs) around the ORR (CR + PR) will be calculated using the Clopper-Pearson method. For patients with measurable disease, a swimmer plot of each patient's overall tumor response assessments during study participation and patient deaths (for those patients who have died) will be presented by cohort.

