# 5. STUDY TREATMENT PRODUCT INFORMATION

For this study, the term "study treatment" refers to the combination of nanatinostat and valganciclovir, except for those patients enrolled into Cohort 3a (nanatinostat monotherapy for the first 6 weeks).

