3.4.1.2 Secondary Efficacy Endpoints

Secondary efficacy endpoints include the following:

- Complete response rate (CRR) defined as the proportion of patients who achieve a CR using the 2007 IWG NHL criteria (Cheson 2007) per IRC review, as well as per Investigator assessment.
- Time to response (TTR) defined as the interval from the start of study drug treatment to the date of first documented CR or PR per IWG criteria. TTR will be determined for response assessments per IRC review as well as by investigator.
- Duration of response (DOR) defined as the interval from the date of first documented CR or PR per IWG criteria to the date of disease progression, death due to any cause, or last adequate (radiographic) response assessment. Dates of disease progression and censoring will be determined as described in Section 4.5.6.2. Duration of response will be determined for response assessments per IRC review as well as by investigator.
- Duration of complete response (DOCR) defined as the interval from the date of first documented CR per IWG criteria to the date of disease progression, death due to any cause, or last adequate (radiographic) response assessment. Dates of disease progression and censoring will be determined as described in Section 4.5.6.2. Duration of complete response will be determined for response assessments per IRC review as well as by investigator.
- Time to next anti-lymphoma treatment (TTNLT) defined as the interval from the start of study drug treatment to the date of next anti-lymphoma treatment (including chemotherapy, radiotherapy, radioimmunotherapy, or immunotherapy). Patients who do not receive subsequent anti-lymphoma treatment will be censored at the date of their last non-missing disease assessment prior to the start of therapy.
- Progression-free survival (PFS) defined as the interval from the start of study drug treatment to the date of first documented disease progression, initiation of new antineoplastic therapy, or death from any cause, whichever occurs first. Dates of disease progression and censoring will be determined as described in Section 4.5.6.2.
- Time to progression (TTP) defined as the interval from the start of study drug treatment to the date of disease progression. Patients whose disease does not progress will be censored at the date of their last tumor assessment.

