4.1.4 Baseline Value

Unless otherwise noted, the baseline value will be defined as the last value reported prior to the first dose of study drug.

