4.5 Efficacy Evaluation

For the Simon 2-stage part of the study, since Cohort 3 (PTCL) patients are initially randomized to monotherapy or combination therapy, their data will be summarized as follows: patients randomized to monotherapy, patients who start on monotherapy and then cross over to combination therapy, and patients randomized to combination therapy.

For the post-Stage 2 expansion part of the study, patients with second-line EBV⁺ lymphoma will also be analyzed separately, and the primary efficacy analyses will be performed in this patient subgroup at the interim analysis (see Section 4.5.6.3 for details of this interim efficacy analysis) and at the final analysis.

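### For Cohort 3a crossover patients the SAP resets the tumor baseline at crossover but makes no matching exception for the time origin of TTR, PFS, TTP, TTNLT and OS

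*SAP*

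**What the plan says.** SAP 4.5 splits Cohort 3 into three efficacy groups: those randomized to monotherapy, "patients who start on monotherapy and then cross over to combination therapy", and those randomized to the combination.

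Three crossover rules are explicit:

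- **Tumor baseline (SAP 4.5.3).** "the CT/PET scan immediately preceding their first dose of combination therapy will be used for their baseline tumor assessment", and not the screening scan. This overrides the general rule in 4.1.4 that "the baseline value will be defined as the last value reported prior to the first dose of study drug".
- **DOR and DOCR (SAP 4.5.4).** They apply only after crossover.
- **Adverse events (SAP 4.6.2).** They are split at the start of combination therapy.

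The time-to-event definitions in SAP 3.4.1.2 have no such rule. TTR is the "interval from the start of study drug treatment to the date of first documented CR or PR per IWG criteria". PFS is the "interval from the start of study drug treatment to the date of first documented disease progression", new antineoplastic therapy or death. TTP is the "interval from the start of study drug treatment to the date of disease progression". TTNLT and OS use the same origin.

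Protocol Section 5 treats "nanatinostat monotherapy for the first 6 weeks" as the study treatment of Cohort 3a. Crossover is open to patients with stable disease at Day 43 and to patients with progression at any time (SAP 3.1 and 3.3.2).

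**The concern.** A column headed as the crossover group will be read as the experience of patients on the combination after monotherapy. Its response rate and DOR do describe that. Followed as written, its TTR, PFS, TTP, TTNLT and OS start at a different point, the first monotherapy dose.

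This has two consequences. Times are lengthened by a monotherapy period that every patient in the column must survive in order to be there. And a patient who crossed over because of progression may already have had the PFS/TTP event, so a later combination response would follow that patient's own progression event in the same column. Cohort 3a exists to separate single-agent from combination activity, and this mixture blurs that separation.

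**Working it through.** The plan gives no figure for this point, so the check compares the two possible origins using the plan's own calendar.

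**Inputs**

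- Duration in days = later date − earlier date + 1; months = days / (365.25/12) (SAP 4.1.5).
- Monotherapy starts on Day 1. The disease assessment is at Week 6 (Day 43), ±7 days (Protocol Table 6).
- Crossover takes place within 7 days of that assessment (Protocol Table 6, footnote 1).
- After crossover, scans occur at the 8-week and 16-week visits as in Cohort 3b (SAP 3.4.1.1). I assume these are counted from the first combination dose. The window is ±7 days, so the first scan falls 49 to 63 days after crossover.
- Cohort 3a has at most 10 patients (SAP 3.3.2).

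**TTR for a response at the first combination scan**

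Let crossover be on Day X and the scan s days later.

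- From the first monotherapy dose: (X + s) − 1 + 1 = X + s.
- From the first combination dose: (X + s) − X + 1 = s + 1.
- Gap: X − 1, whatever the scan date.

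Nominal case, X = 43 and s = 56: 43 + 56 = **99 days** (3.25 months) against 56 + 1 = **57 days** (1.87 months). The gap is 42 days.

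| Crossover day | s = 49 / 56 / 63: from monotherapy | From combination | Gap |
|---|---|---|---|
| 36 (scan 7 days early, same-day crossover) | 85 / 92 / 99 | 50 / 57 / 64 | 35 |
| 43 (nominal) | 92 / 99 / 106 | 50 / 57 / 64 | 42 |
| 57 (scan 7 days late, then 7 days) | 106 / 113 / 120 | 50 / 57 / 64 | 56 |

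The gap is shorter if progression leads to crossover before Day 36. It would be longer for a monotherapy responder who progresses and crosses over later.

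**PFS and TTP, crossover on progression at the Day 43 scan**

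The event time is 43 − 1 + 1 = 43 days, and 43 / 30.4375 = 1.41 months. The combination starts between Day 43 and Day 50, so the event falls 0 to 7 days before the first combination dose. A combination response at Day 99 would come 99 − 43 = 56 days after that patient's PFS event.

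**PFS and TTP, crossover with stable disease**

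There is no event before crossover. A later event on Day D is timed at D days instead of D − X + 1. The excess is again X − 1, which is 42 days nominally and 35 to 56 with the windows.

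**Does another rule fill the gap?**

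SAP 4.5.6.2 censors for non-protocol anti-cancer treatment. Crossover is protocol treatment, so that rule does not apply to it.

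**What is not touched**

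The Simon rule (at least 2 of 10, then at least 5 of 21) has rejection probability Σ P(X₁ = x) · P(X₂ ≥ max(0, 5 − x)) over x = 2 to 10, with X₁ ~ Bin(10, p) and X₂ ~ Bin(11, p). This gives 0.0440 at p = 0.10 and 0.8615 at p = 0.35, matching the stated 0.0440 and 86.2%. Nothing in it depends on the crossover group.

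**The case against.** **The SAP never says that the clock stays at monotherapy start.** This is true. SAP 3.1 says treatment starts on Cycle 1 Day 1, and crossover patients have a second Cycle 1 Day 1 for the combination, so a reader could place the origin there. That reading is the weaker one. SAP 3.3.2 places randomization at drug dispensation for Cycle 1 Day 1, which for Cohort 3a is the monotherapy start, and Protocol Section 5 counts monotherapy as study treatment. If both readings are allowed, the choice would be made with open-label data in view, which the SAP's introduction says it aims to avoid.

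**The 99-day figure rests on an assumption.** This stands. Protocol 7.3.1.2 counts scans by calendar from the first dose. If that were applied to the monotherapy dose, the Week 8 scan would fall on Day 57, and TTR would be 57 days from monotherapy and 57 − 43 + 1 = 15 days from combination. SAP 3.4.1.1 favors counting from combination start without naming the origin. The 42-day gap between the two origins is the same either way.

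**A reader might infer that TTR is inflated by at least six weeks.** Six weeks is not a minimum, because the scan window and earlier progression both allow a shorter gap.

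**A reader might infer that every crossover patient, or every one who progressed, has a PFS/TTP event before combination therapy.** The documents do not support this. Stable-disease crossovers have no such event. Protocol 7.3.1.2 assigns PFS and TTP to the IRC and leaves patient management to the Investigator, so progression that led to crossover but that the IRC does not confirm is not an IRC event.

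**The impact is small.** This also stands. The results are descriptive, and the swimmer plot (SAP 4.5.3) and the listing of derived measures (4.5.4) would let a reader recover much of the timing patient by patient.

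**Conclusion.** The inconsistency is real and minor. For the crossover group, the response reference moves to crossover while the written origin for TTR, PFS, TTP, TTNLT and OS does not.

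For crossover at about Day 43 the difference is 42 days, with a range of 35 to 56. The comparison of 99 with 57 days also assumes that post-crossover scans are counted from the first combination dose. Patients who cross over on IRC-confirmed progression have a PFS/TTP event before combination therapy. The split between stable-disease and progression crossovers is not given, so they number anywhere from 0 to 10.

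It would be wrong to conclude that the primary analysis or the cohort decisions are compromised. At most 10 patients and descriptive secondary endpoints are involved, Cohort 3a does not expand, and the Cohort 3b Simon decision does not use these data.

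**What to change.** Add the following to SAP 4.5.4:

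- **Crossover group.** TTR, PFS, TTP, TTNLT and OS start at the first combination dose. Progression is judged against the crossover baseline of SAP 4.5.3.
- **Randomized-to-monotherapy group.** Keep the first monotherapy dose as origin and count progression on monotherapy as the PFS/TTP event. State how crossover without progression is handled, for example by censoring at the last assessment before the first combination dose.

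It would also help to state in SAP 3.4.1.1 that the 8-week and 16-week scans after crossover are counted from the first combination dose, if that is what is meant.

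The cost is a few lines of SAP text and one derivation flag. Data collection, scan timing and treatment do not change.

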4.5.4 Secondary Endpoint Analysis Methods

The ORR per investigator assessment, CRR per IRC review, and CRR per investigator assessment will be summarized using the same methods as described for the primary efficacy endpoint.

Time to response, DOR, DOCR, TTNLT, TTP, PFS, and OS will be summarized in days using Kaplan-Meier (KM) methodology. The number of patients who experienced the event of interest and the number of patients censored will be presented; as will KM product limit estimates of the median with associated CIs (where estimable) using Greenwood's formula. The range for all patients, as well as those who experience the event of interest will also be summarized. Kaplan-Meier estimates of the survival distribution function for DOR, PFS, and OS over time will be generated and all derived efficacy measures will also be provided in a separate listing.

For Cohort 3a patients who crossover to receive combination therapy, DOR and DOCR will only be applicable after crossover given the requirement that patients only cross over from monotherapy to combination therapy after stable disease at the Day 43 visit (or progressive disease at any time).

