4.5.6.2 Handling of Dropouts or Missing Data

Overall response is based on those patients with available data (baseline and post-baseline response assessment). Non-evaluable patients are considered non-responders and will be included in the denominator. Progression-free survival and DOR will be right-censored for patients who meet one of the following conditions: 1) non-protocol systemic anti-cancer treatment started before documentation of disease progression or death, 2) death or disease progression after more than one missed disease assessment visit, or 3) alive and does not have documentation of disease progression before a data analysis cutoff date. These conventions are based on the FDA Guidance for Industry, Clinical Trial Endpoints for the Approval of Cancer Drugs and Biologics (2018) and Clinical Trial Endpoints for the Approval of Non-Small Cell Lung Cancer Drugs and Biologics (2015). The analyses of PFS and DOR will be right-censored according to the conventions described in the table below.

Table 3 Censoring Conventions for Progression-Free Survival, Time to Progression, and Duration of Response

Situation	Date of Progression for Censoring	Outcome
No baseline tumor assessments	Randomization (if applicable) or enrollment	Censored
New anti-cancer therapy started before documentation of PD or death	Date of last disease assessment prior to start of new anti-cancer therapy	Censored*
Death or PD immediately after more than one consecutively missed disease assessment visit	Date of last disease assessment visit without documentation of PD that is before the first missed visit	Censored
Alive and without PD documentation	Date of last disease assessment	Censored
Death or PD between planned disease assessments	Date of death or first disease assessment showing PD, whichever occurs first	Progressed

Situation	Date of Progression for Censoring	Outcome
Death before first disease assessment	Date of death	Progressed

*PFS, TTP, DOR will additionally be analyzed without censoring for hematopoietic stem cell transplant

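### Time to response is summarized by Kaplan-Meier with no stated population or censoring rule, so its median and CI may not describe when responders respond

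*SAP*

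**What the plan says.** SAP 3.4.1.2 gives TTR as "defined as the interval from the start of study drug treatment to the date of first documented CR or PR per IWG criteria", to be derived from both IRC and investigator assessments. SAP 4.8 lists it among the secondary endpoints that the SAP adds to the protocol.

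The analysis is in SAP 4.5.4: "Time to response, DOR, DOCR, TTNLT, TTP, PFS, and OS will be summarized in days using Kaplan-Meier (KM) methodology". For every endpoint in that list, "The number of patients who experienced the event of interest and the number of patients censored will be presented", together with "KM product limit estimates of the median with associated CIs (where estimable) using Greenwood's formula". The section adds: "The range for all patients, as well as those who experience the event of interest will also be summarized". Curves are narrower in scope: "Kaplan-Meier estimates of the survival distribution function for DOR, PFS, and OS over time will be generated".

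On censoring, 3.4.1.2 states a rule for TTNLT, TTP and OS, and refers to 4.5.6.2 for DOR, DOCR and PFS. TTR gets neither. The table in 4.5.6.2 is titled "Censoring Conventions for Progression-Free Survival, Time to Progression, and Duration of Response" and does not mention TTR.

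**The concern.** TTR starts at first dose, so every treated patient has a start date whether or not a response follows. DOR and DOCR start at a response and are restricted to responders by construction. TTR is not. The censored count, and the separate ranges for all patients and for those with the event, make sense for TTR only if non-responders are in the analysis as censored observations. In a responders-only analysis the censored count would be zero and the two ranges would coincide.

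The likely default censoring date is the last disease assessment. Scheduled scans run until progression (Protocol 6.1, Table 5 footnotes) or new anti-lymphoma therapy (Protocol 7.2.6), and treatment generally stops at progression (SAP 3.1). For a progressor, the last assessment is therefore roughly the progression scan. Kaplan-Meier then assumes that this patient had the same future chance of responding as patients still on drug. Progression and death in fact remove that chance or nearly so.

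At stake is a secondary endpoint whose median and CI would answer no clear question and could sit awkwardly beside the ORR for the same patients. SAP 4.5.6.3 asks for point and interval estimates of secondary endpoints at the interim as well.

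**Working it through.** The SAP states no numeric figure for TTR. Its nearest figures on response, the two-stage type I error of 0.0440 and power of 86.2%, reproduce (0.0440 and 86.15%) but play no part below.

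**Inputs from the documents.**
- ORR 33.3%: PTCL Stage 2 estimate, SAP 4.7. The earlier Phase 1b/2 study had 18/50 = 36%, Protocol 1.2.4.
- N = 120: expansion size, SAP 4.7. This gives 40 responders and 80 non-responders.
- Scans at Weeks 8, 16 and 24, then every 12 weeks: Protocol 7.3.1.2.
- Most responses in the earlier study were seen by the first assessment, Protocol 1.2.4. The share is not given.
- Median PFS of 3.7 months with chemotherapy at relapse of PTCL, Protocol 1.1.2. In weeks, 3.7 × (365.25/12)/7 = 16.1. This is only a loose anchor, because it covers responders too.

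**Assumed.** The split of responses across scans, and when non-responders leave. The documents give neither, so ranges are used.

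**Formula.** S = product over scans of (1 − responses / number at risk), with non-responders removed from the risk set when they progress or die. The cumulative incidence of response, with those exits as competing events, is responses / 120.

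**Hand example.** Responses at Weeks 8/16/24 are 28/8/4; progressions or deaths are 50/20/4. Risk sets: 120; 120 − 28 − 50 = 42; 42 − 8 − 20 = 14.

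S = (1 − 28/120)(1 − 8/42)(1 − 4/14) = 0.7667 × 0.8095 × 0.7143 = 0.443, so 1−KM = 0.557. S is 0.7667 × 0.8095 = 0.621 after Week 16 and falls below 0.5 at Week 24, so the KM median is Week 24. Cumulative incidence is 40/120 = 0.333, with no all-patient median. Among responders, 28/40 = 70% respond at Week 8, so their median is Week 8.

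| Responses, Wk 8/16/24 | Progressions or deaths | At risk | 1−KM | KM median |
|---|---|---|---|---|
| 28/8/4 | 50/20/4 | 120/42/14 | 0.557 | Week 24 |
| 30/8/2 | 30/20/10 | 120/60/32 | 0.391 | not reached |
| 25/10/5 | 55/15/5 | 120/40/15 | 0.604 | Week 24 |

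**Wider grid.** True ORR is 33.3%. Non-responders' time to progression is exponential with the median shown, and 25% of them leave between scans. Entries are the final 1−KM, with the KM median in brackets where it is reached.

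| Non-responder median | 50% of responses at Wk 8 | 70% | 90% |
|---|---|---|---|
| 6 weeks | 0.72 (Wk 24) | 0.63 (Wk 24) | 0.49 |
| 8 weeks | 0.60 (Wk 24) | 0.53 (Wk 36) | 0.43 |
| 12 weeks | 0.49 | 0.45 | 0.39 |
| 16 weeks | 0.44 | 0.41 | 0.37 |

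Cumulative incidence is 0.333 in every cell. A KM median appears in 4 of 12.

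**Readings that remove the excess.** With responses of 28/8/3/1 at Weeks 8/16/24/36 and non-responders held at risk to the end of follow-up, S = (92/120)(84/92)(81/84)(80/81) = 80/120, so 1−KM = 0.333. With responders only there is no censoring, and the median is Week 8. The SAP specifies neither.

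**The case against.** The best defence is that the SAP nowhere says that non-responders are censored at progression. The wording on censored counts and ranges covers seven endpoints at once, two of which are responder-only, and the absence of a TTR censoring rule fits an analysis in which nobody is censored. A median is promised only where estimable. The number of responders is shown beside it, so a reader could see that most patients did not respond. The earlier study's early responses point toward the low end of the grid. All results are described as descriptive (SAP 4.5.6.1 and 4.5.6.5).

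Much of this stands. Censoring at progression is an inference, and the consequence is small. It does not rescue the text, because the readings that avoid the problem are not written either, and the one method named gives a misleading median on the most natural reading.

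Some stronger readings are tempting, and the documents do not support them.
- A reader might infer that the drug's response rate will be reported too high. No KM curve is planned for TTR, so 1−KM is not itself a listed output. ORR is a simple proportion with a Clopper-Pearson interval (SAP 4.5.3), and non-evaluable patients count as non-responders (SAP 4.5.6.2).
- A reader might infer that the summary flatters the drug. In the hand example the KM median is Week 24 against Week 8 among responders, which makes response look slower.
- A reader might infer that most patients progress before responding. An ORR of 33% to 36% says only that about two-thirds do not respond, and some of those may have stable disease.
- A reader might infer that the excess vanishes if every response comes at the first scan. If 20 of 120 leave before Week 8 and all 40 responses occur then, 1−KM = 40/100 = 0.40.

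**Conclusion.** The point holds as a limited one. The SAP applies Kaplan-Meier, with a censored count, median and CI, to an endpoint whose population and censoring it does not define. If all patients are included and non-responders are censored at last assessment, the TTR median and CI do not describe when responders respond and can be inconsistent with the ORR. At an ORR of 33.3% the implied 1−KM is about 0.37 to 0.72 over the assumed timings. With 90% of responses at Week 8 it is 0.37 to 0.49 and no median is reached.

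These sizes rest on assumed response and progression times and on the inferred censoring date. The damage stops at the descriptive TTR median and CI. The primary ORR, the Stage 1 and Stage 2 gates and the interim threshold of 26 responses in 40 patients all use response counts and are untouched. Severity is low to moderate, and this is a cheap improvement.

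**What to change.** In SAP 4.5.4, take TTR out of the Kaplan-Meier list and state that it is summarized among responders only, by IRC and by investigator: n, median, quartiles and range. Make the definition in 3.4.1.2 match.

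If an all-patient summary is also wanted, specify the cumulative incidence of response with progression, death and new anti-cancer therapy as competing events. In the calculations above this levels off at the ORR.

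The cost is one SAP sentence, with no added programming for the responders-only version. No new data are needed. The cumulative incidence option would add one further output.
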